8.3.6.1. Pregnancy Testing

Serum pregnancy tests are required for all women of childbearing potential during screening and either EOT or the safety follow-up visit 28 days after the last dose. Pregnancy testing is required on Day 1 of all cycles and can be either serum- or urine-based and will be performed before administration of study treatment. If a pregnancy test is performed during screening within 7 days of Cycle 1 Day 1, it is not necessary to repeat on Cycle 1 Day 1 (unless necessary based on country-specific requirements).

A positive urine pregnancy should be confirmed with a serum pregnancy test. If a pregnancy is confirmed by a serum pregnancy test, see Section 9.7.

Timing and type of pregnancy testing may be adjusted based on country-specific requirements.

Table 12: **Required Laboratory Analytes**

Serum Chemistries	Hematology	Urinalysis With Microscopic Examination	Coagulation	Pregnancy Testing
Albumin Alkaline phosphatase ALT AST Amylase Bicarbonate or CO ₂ ^a Blood urea nitrogen or urea ^a Calcium Chloride	Complete blood count, including: • Hemoglobin • Hematocrit • Platelet count • Red blood cell count • WBC count Differential count,	Color and appearance pH and specific gravity Bilirubin Glucose Ketones Leukocytes Nitrite Occult blood Protein	PT PTT or aPTT INR	Women of childbearing potential
Creatinine	including:	Lipid Panel (Fasting)	Endocrine Function	HIV Management
Glucose Lactate dehydrogenase Lipase Phosphate Potassium Sodium Total bilirubin Direct bilirubin (if total bilirubin is elevated above ULN) Total protein Uric acid	 Basophils Eosinophils Lymphocytes Monocytes Neutrophils Absolute values must be provided for: WBC differential laboratory results 	Total cholesterol Triglycerides LDL HDL	Thyroid-stimulating hormone (TSH) Thyroxine (T4/FT4) ^a Triiodothyronine (T3/FT3) ^a	Only applicable for participants known to be HIV-positive HIV viral load CD4+ cell count

Note: Additional tests may be required, as agreed by investigator and sponsor, based on emerging safety data. ^a If considered standard by the region.

8.4. Pharmacokinetic Assessments

Assessment of PK is an important objective of this study, representing the first clinical experience with administration of INCMGA00012 as a 30-minute infusion. Blood samples for PK analysis will be obtained at the visits and timepoints indicated in Table 4.

After the preinfusion PK sample is drawn, participants will begin the study drug infusion. Adjustments to the timing of blood sampling may be made based on emerging PK data. The exact dates and times of the PK blood collection will be recorded in the eCRF. Instructions for sample preparation and shipping will be provided in the Laboratory Manual.

8.5. Pharmacodynamic Assessments

8.5.1. Description of Analyses

Additional optional specimens may be collected at any time during study to assess changes associated with safety, efficacy, or resistance to treatment.

Analyses will be conducted by Incyte Corporation (Wilmington, DE) or Incyte's designee. The collection schedule is found in Table 4.

8.6. Unscheduled Visits

Unscheduled study visits may occur at any time if medically warranted. Any assessments performed at those visits should be recorded in the eCRF.

8.7. End of Treatment and/or Early Termination

Once a participant permanently discontinues study treatment, the EOT visit should be conducted, and the data should be entered in the EOT visit in the eCRF. If the EOT visit coincides with a regular study visit, the EOT evaluations will supersede those of that scheduled visit. Should study treatment discontinuation occur < 21 days after the final dose of study treatment, a 28-day safety follow-up visit is required and should be conducted according to Table 3. If the EOT visit occurs ≥ 21 days after the last study treatment, only a single EOT/28-day safety follow up is required; otherwise, the EOT visit will also serve as the 28-day safety follow-up visit, and the EOT assessment schedule will be followed.

8.8. Follow-Up

The study design includes a follow-up period for participants subsequent to the end of the study treatment period. After discontinuation of study treatment, all study participants continue in the follow-up period of the study.

8.8.1. Safety Follow-Up

The safety follow-up period starts once the participant discontinues study treatment. Approximately 28 days after the final dose of study drug (\pm 7 days), participants are to attend a clinical visit for a safety evaluation. During this visit, blood will be collected for safety laboratory analysis, a physical exam will be performed, and AEs and concomitant medications will be assessed according to the scheduled assessments found in Table 3. Participants will be followed for irAEs for 90 days after the last dose of study drug or until the participant begins a new anticancer therapy, whichever occurs first. If a participant is scheduled to begin a new anticancer therapy before the end of the 28-day safety follow-up period, the safety follow-up visit should be performed before the new anticancer therapy is started.

9. ADVERSE EVENTS: DEFINITIONS AND PROCEDURES FOR RECORDING, EVALUATING, FOLLOW-UP, AND REPORTING

9.1. Definition of Adverse Event

Adverse Event Definition

- An AE is any untoward medical occurrence associated with the use of a drug in humans, whether or not considered drug-related.
- An AE can therefore be any unfavorable and unintended sign (including an abnormal laboratory finding), symptom, or disease (new or exacerbated) temporally associated with the use of study drug.

Events Meeting the Adverse Event Definition

- Any safety assessments (eg, ECG, vital signs measurements), including those that worsen from baseline, considered clinically significant in the medical and scientific judgment of the investigator (ie, not related to progression of underlying disease).
- Abnormal laboratory test results constitute an AE if they are considered clinically meaningful, induce clinical signs or symptoms, require concomitant therapy, or require changes in study drug. Whenever possible, a diagnosis (eg, anemia, thrombocytopenia) should be recorded in the eCRF rather than the abnormal lab result (eg, low hemoglobin, platelet count decreased).
- Exacerbation of a chronic or intermittent pre-existing condition including either an increase in frequency and/or intensity of the condition.
- New conditions detected or diagnosed after study drug administration even though they may have been present before the start of the study.
- Signs, symptoms, or the clinical sequelae of a suspected drug-drug interaction.
- Signs, symptoms, or the clinical sequelae of a suspected overdose of either study drug or a concomitant medication. Overdose per se will not be reported as an AE/SAE unless it is an intentional overdose taken with possible suicidal/self-harming intent. Such overdoses should be reported regardless of sequelae.

Events **NOT** Meeting the Adverse Event Definition

- Any clinically significant abnormal laboratory findings or other abnormal safety assessments that are associated with the underlying disease, unless judged by the investigator to be more severe than expected for the participant's condition.
- The disease/disorder being studied or expected progression, signs, or symptoms of the disease/disorder being studied, unless more severe than expected for the participant's condition or considered to be treatment-related by the investigator.
- Efficacy endpoints as outlined in Section 3 will not be reported as AE/SAEs, specifically, any event that is related to disease progression of the cancer under study. Unblinded aggregated efficacy endpoint events and safety data will be monitored to ensure the safety of the participants in the study. Any suspected endpoint that upon review is not progression of the cancer under study will be forwarded to Incyte Pharmacovigilance as a SAE within 24 hours of determination that the event is not progression of the cancer under study.
- Medical or surgical procedure (eg, endoscopy, appendectomy): the condition that leads to the procedure is the AE if it occurred after signing informed consent. If present before entering the study, the condition should be captured as medical history.
- Situations in which an untoward medical occurrence did not occur (social and/or convenience admission to a hospital).
- Anticipated day-to-day fluctuations of pre-existing disease(s) or condition(s) present or detected at the start of the study that do not worsen.

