9.2. Definition of Serious Adverse Event

If an event is not an AE per definition above, then it cannot be an SAE even if serious conditions are met (eg, hospitalization for signs/symptoms of the disease under study, death due to progression of disease).

A Serious Adverse Event is defined as any untoward medical occurrence that, at any dose:

a. Results in death

b. Is life-threatening

The term 'life-threatening' in the definition of 'serious' refers to an adverse drug experience that places the participant, in the opinion of the initial reporter, at immediate risk of death from the adverse experience as it occurred. This does not include an adverse drug experience that, had it occurred in a more severe form, might have caused death.

c. Requires inpatient hospitalization or prolongation of existing hospitalization

In general, hospitalization signifies that the participant has been detained (usually involving at least an overnight stay) at the hospital or emergency ward for observation and/or treatment that would not have been appropriate in the physician's office or outpatient setting. Complications that occur during hospitalization are AEs. If a complication prolongs hospitalization or fulfills any other serious criteria, the event is serious. When in doubt as to whether "hospitalization" occurred or was necessary, the AE should be considered serious.

Hospitalization for elective treatment of a pre-existing condition that did not worsen from baseline is not considered an AE.

d. Results in persistent or significant disability/incapacity

- The term disability means a substantial disruption of a person's ability to conduct normal life functions.
- This definition is not intended to include experiences of relatively minor medical significance, such as uncomplicated headache, nausea, vomiting, diarrhea, influenza, and accidental trauma (eg, sprained ankle), that may interfere with or prevent everyday life functions but do not constitute a substantial disruption.

e. Is a congenital anomaly/birth defect

f. Other situations (Important Medical Event)

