4.1.7. On-Treatment Assessment/Event

Safety summaries and selected summaries of deaths will summarize only on-treatment assessments/events. On-treatment assessment/event is defined as any assessment/event obtained in the time interval:

 Date of first infusion of INCMGA00012 through date of last infusion of INCMGA00012 + 90 days;

Adverse events that begin or worsen after informed consent obtained should be recorded in the Adverse Events CRF.

If the last date of study drug administration is missing, on-treatment assessments/events include any assessment/event recorded in the database and those that occur after the start date of study drug unless there are other datasets indicating treatment is ended.

Data listings will include all assessments/events, flagging those that are not on-treatment assessments/events.

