8.2.3. Adverse Event Summaries

An overall summary of AEs may include the following:

- Number (%) of participants reporting any TEAEs
- Number (%) of participants reporting any serious TEAEs
- Number (%) of participants reporting any Grade 3 or higher TEAEs
- Number (%) of participants reporting any TEAEs related to study drug
- Number (%) of participants reporting any serious TEAEs related to study drug
- Number (%) of participants reporting any Grade 3 or higher TEAEs related to INCMGA00012
- Number (%) of participants who temporarily interrupted study drug infusion because of TEAEs
- Number (%) of participants who delayed next scheduled dose because of TEAEs
- Number (%) of participants who permanently discontinued INCMGA00012 because of TEAEs
- Number (%) of participants who had a fatal TEAE
- Number (%) of participants who withdrew from study because of TEAEs The following summaries may be produced by MedDRA term:
- Summary of TEAEs by SOC and PT
- Summary of TEAEs by PT in decreasing order of frequency
- Summary of TEAEs by SOC, PT, and maximum severity
- Summary of Grade 3 or higher TEAEs by SOC and PT
- Summary of Grade 3 or higher TEAEs by PT in decreasing order of frequency
- Summary of serious TEAEs by SOC and PT
- Summary of serious TEAEs by PT in decreasing order of frequency
- Summary of treatment-related TEAEs by SOC and PT
- Summary of treatment-related TEAEs by PT in decreasing order of frequency
- Summary of treatment-related Grade 3 or higher TEAEs by SOC and PT

- Summary of treatment-related serious TEAEs by SOC and PT
- Summary of TEAEs with a fatal outcome by SOC and PT
- Summary of TEAEs leading to infusion interruption by SOC and PT
- Summary of TEAEs leading to infusion delay in next scheduled dose by SOC and PT
- Summary of leading to study drug discontinuation by SOC and PT
- Summary of infusion-related reactions by SOC and PT
- Signs/symptoms of infusion-related reactions
- Summary of nonserious TEAEs by PT in decreasing order of frequency The following summaries for AEs of special interest will be included:
- Overall summary of TEAEs of special interest
- Summary TEAEs of special interest by group term and PT
- Summary TEAEs of special interest by group term, PT, and maximum severity
- Summary of Grade 3 or higher TEAEs of special interest by group term and PT
- Summary of TEAEs of special interest with a fatal outcome by group term and PT

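### Protocol 9.1 keeps unusually severe or drug-attributed progression as an adverse event in one bullet and bars all progression-related events in the next, so such cases can be left out of SAE reporting and TEAE counts

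*Protocol*

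**What the plan says.** Protocol 9.1 opens broadly: "An AE is any untoward medical occurrence associated with the use of a drug in humans, whether or not considered drug-related". It then lists events that do not meet the definition, and two adjacent bullets in that list matter here.

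- **Studied-disease bullet.** The cancer under study and its expected progression, signs or symptoms are not AEs, "unless more severe than expected for the participant's condition or considered to be treatment-related by the investigator".
- **Endpoint bullet.** The efficacy endpoints of Section 3 "will not be reported as AE/SAEs, specifically, any event that is related to disease progression of the cancer under study". The bullet adds a safeguard: "Unblinded aggregated efficacy endpoint events and safety data will be monitored to ensure the safety of the participants in the study". It gives one route back into reporting: "Any suspected endpoint that upon review is not progression of the cancer under study will be forwarded to Incyte Pharmacovigilance as a SAE". The time limit for that step is 24 hours.

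Protocol 9.2 states: "If an event is not an AE per definition above, then it cannot be an SAE even if serious conditions are met". Death from progression is one of its examples. Protocol 9.4 requires SAEs to be reported within 24 hours whatever the suspected cause.

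SAP 8.2.1 defines a TEAE as an AE that is new or worsens after the first dose. SAP 8.2.3 lists counts of serious, related and Grade 3 or higher TEAEs, and "Number (%) of participants who had a fatal TEAE". SAP 4.1.7 adds: "Safety summaries and selected summaries of deaths will summarize only on-treatment assessments/events".

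**The concern.** A progression that the investigator attributes to the drug, or that is worse than expected, meets the first bullet's exception and the second bullet's bar at the same time. One makes it reportable, and serious if a seriousness criterion is met. The other says not to report it.

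Safety is a secondary endpoint (Protocol Section 3), and the text governs more than tabulation. It also decides whether a suspected drug-related case reaches the sponsor as an SAE. Under the endpoint bullet, any error goes one way: it lowers the serious, related and fatal counts.

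The situation is not remote for this drug class. Protocol 8.2.2 says that a response to immunotherapy may follow an initial rise in tumor burden or new lesions, and Protocol 4.1 allows treatment beyond conventional RECIST progression. Sites can therefore meet events that raise both progression and drug effect.

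**Working it through.** The documents state no figure for this point, so the main check is textual.

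**1. The two bullets side by side**

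| Event | Studied-disease bullet | Endpoint bullet | Agree? |
|---|---|---|---|
| Expected progression, not attributed to the drug | Not an AE | Not reported | Yes |
| Suspected endpoint found on review not to be progression | Does not apply | Sent to the sponsor as an SAE | Yes |
| Progression more severe than expected | Stays an AE | Not reported | No |
| Progression attributed to treatment by the investigator | Stays an AE | Not reported | No |

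The endpoint bullet's route back serves only the second row. For the last two rows the event is progression, so that route is closed. No rule of precedence appears in Protocol 9.1 to 9.4 or in SAP 8.2.

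**2. How the endpoint-bullet reading carries through**

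- Protocol 9.2: an event that is not an AE cannot be an SAE, even if fatal.
- Protocol 9.4: the 24-hour rule ignores causality, but applies only to events that already qualify as SAEs.
- SAP 8.2.1: missing causality counts as related, and AEs count as treatment-emergent unless that can be clearly ruled out. Both defaults act only on AEs already recorded.
- SAP 8.2.3: serious, related and fatal counts are subsets of recorded TEAEs.

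**3. What one case is worth**

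Inputs: about 30 participants per cohort and about 120 in total (Protocol Table 2). The number of affected participants, x, is an assumption, because the documents give none.

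Shift per case = 1/n: 1/30 = 3.3 percentage points; 1/120 = 0.8 points.

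Exact 95% limits: lower = 2.5% quantile of Beta(x, n − x + 1), or 0 when x = 0; upper = 97.5% quantile of Beta(x + 1, n − x). As a check, this formula returns all six intervals in Protocol Table 13, for example 3/30: 2.1, 26.5 and 12/30: 22.7, 59.4.

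| Assumed x | Cohort of 30: % (95% CI) | Pooled 120: % (95% CI) |
|---|---|---|
| 0 (none reported) | 0 (0, 11.6) | 0 (0, 3.0) |
| 1 | 3.3 (0.1, 17.2) | 0.8 (0.0, 4.6) |
| 2 | 6.7 (0.8, 22.1) | 1.7 (0.2, 5.9) |
| 3 | 10.0 (2.1, 26.5) | 2.5 (0.5, 7.1) |

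The rows count this type of event only, not all serious or fatal TEAEs. They show scale and do not predict frequency.

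**The case against.** The strongest reply is that the bullets can be read together. The endpoint bullet's subject is the efficacy endpoints of Section 3. It may mean only that a RECIST progression or a PFS or OS event is not in itself an AE, which leaves the more specific exception to govern unusual or drug-attributed presentations. That reading is possible, but the text does not compel it. The bullet reaches any event related to progression, and the studied-disease bullet itself names progression. A site should not have to infer the boundary.

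Several other points on this side stand, and they limit what can be claimed.

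- **Section 9.2 is not a second contradiction.** It is conditional on 9.1 and inherits whatever 9.1 means.
- **The events do not disappear from the study data.** Progression and death feed PFS and OS (SAP 7.3.3.3 and 7.3.3.4). A reader might infer that no output would reveal early deaths. SAP Appendix A does not support this: it plans an OS table (2.2.3), OS curves by cohort (Figure 4.3) and a listing of OS events (2.6.1). What it does not name is a tabulation of deaths by cause. Even that is weak evidence of an omission, because the appendix calls its lists guidelines and refers to standard safety tables held elsewhere.
- **Oversight exists.** Protocol 2.3 describes safety team meetings and contact with investigators. Aggregate unblinded monitoring is consistent with an open-label study and is not a defect.

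These sources still do not replace AE reporting. PFS and OS, as the SAP describes them, carry dates and status, not the investigator's view of causality or severity. Aggregate monitoring does not return a single case to the AE data. Under Protocol 4.1, survival follow-up also ceases to be required, once the primary efficacy analysis is complete, for participants who are off study drug.

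**Conclusion.** The conflict is real but narrow. For progression that is worse than expected or attributed to treatment, Protocol 9.1 gives opposite instructions in adjacent bullets, with no rule to choose between them. If a site applies the endpoint bullet literally, such a case can be missing from SAE reporting and from the serious, related and fatal TEAE counts.

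The only size the documents support is per case: 3.3 points in a cohort of 30 or 0.8 points in 120. A reader might go further and assume that some percentage of participants is affected, and so that related-serious or fatal rates are wrong by several points. The documents give no frequency. Such a figure would also require every event to be serious and related (or fatal), and every site to follow the endpoint bullet.

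ORR, the primary endpoint, is unaffected. This is an ambiguity in a reporting definition that reaches the safety tables, not an error in the SAP's counting rules. It is worth correcting because the remedy is small and the possible loss goes in one direction.

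**What to change.** Reconcile the two bullets in Protocol 9.1. The simplest way is to end the endpoint bullet's bar on progression-related events with the exception the protocol already states one bullet earlier: "unless more severe than expected for the participant's condition or considered to be treatment-related by the investigator". This adds no new reporting policy. The 9.2 example then follows from 9.1 and needs no separate rule.

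Optionally, add to SAP 8.2.3 and Appendix A a table of on-treatment deaths by cause. First confirm that the eCRF records cause of death: SAP 7.3.3.3 and 7.3.3.4 cite the Death Report eCRF only for the date.

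Costs: one clause, which needs IRB/IEC approval as a protocol amendment (Protocol 11.1), perhaps a few more SAE reports, and slightly higher serious and fatal TEAE rates. The clause acts forward only. Amendment 4 records that the last participant was enrolled in April 2020, so cases that sites have already left out can be recovered only by querying them.

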9.2. Definition of Serious Adverse Event

If an event is not an AE per definition above, then it cannot be an SAE even if serious conditions are met (eg, hospitalization for signs/symptoms of the disease under study, death due to progression of disease).

A Serious Adverse Event is defined as any untoward medical occurrence that, at any dose:

a. Results in death

b. Is life-threatening

The term 'life-threatening' in the definition of 'serious' refers to an adverse drug experience that places the participant, in the opinion of the initial reporter, at immediate risk of death from the adverse experience as it occurred. This does not include an adverse drug experience that, had it occurred in a more severe form, might have caused death.

c. Requires inpatient hospitalization or prolongation of existing hospitalization

In general, hospitalization signifies that the participant has been detained (usually involving at least an overnight stay) at the hospital or emergency ward for observation and/or treatment that would not have been appropriate in the physician's office or outpatient setting. Complications that occur during hospitalization are AEs. If a complication prolongs hospitalization or fulfills any other serious criteria, the event is serious. When in doubt as to whether "hospitalization" occurred or was necessary, the AE should be considered serious.

Hospitalization for elective treatment of a pre-existing condition that did not worsen from baseline is not considered an AE.

d. Results in persistent or significant disability/incapacity

- The term disability means a substantial disruption of a person's ability to conduct normal life functions.
- This definition is not intended to include experiences of relatively minor medical significance, such as uncomplicated headache, nausea, vomiting, diarrhea, influenza, and accidental trauma (eg, sprained ankle), that may interfere with or prevent everyday life functions but do not constitute a substantial disruption.

e. Is a congenital anomaly/birth defect

f. Other situations (Important Medical Event)

An event that may not result in death, be immediately life-threatening, or require hospitalization, but may be considered serious when, based on appropriate medical judgment, the event may jeopardize the participant and may require medical or surgical intervention to prevent one of the outcomes listed in the above definition. Examples of such events include invasive or malignant cancers (excluding the disease[s] under study in oncology protocols), intensive treatment in an emergency department or at home for allergic bronchospasm, blood dyscrasias, or convulsions that do not result in hospitalization, or development of drug dependency or drug abuse.

